Blood draws (Aim 1 only). The total amount of blood drawn for the purposes of the study will be depend on the study. The potential risks include infection at the site of the blood draw. Careful sterile technique will minimize the chances of infection at the blood draw site. There is a risk for redness, itching, bruising and soreness at the blood draw site. Your blood will be drawn from a site on your arm. Additional blood may be drawn during surgery as determined by the hospital staff and/or doctors outside the purpose of this research study.

Aim 1 (N=40, 20/group) and **Aim 2 (N=80, 40/group)** will have the same total amount of blood drawn, at study intervals.

Muscle biopsy. Biopsies will be collected from all TKA patients (Aim 2 patients will have the choice to participate with or without muscle biopsies).

- **Aim 1 (N=40, 20/group)** will have 1 muscle and 1 fat biopsy per leg during TKA (in the OR) (N=40) and at 1 week post-TKA (N=20); or 2 weeks post-TKA (N=20).
- **Aim 2 (N=80, 40/group)** will have 1 muscle biopsy per leg at Baseline, 6wk & 6mopost-TKA.

The biopsies will be obtained from the vastus lateralis using a 5mm Bergstrom biopsy needle with applied suction under sterile conditions. A single incision of 0.5 cm will be made in the skin down to the level of the fascia, and approximately 150 mg of muscle tissue will be removed during each biopsy.

The potential risks are pain, bleeding, infection, and loss of superficial sensation (light touch, hot/cold) to an area around the biopsy site. There will be a scar approximately 0.6 cm long. The risk of bleeding from the biopsy site is 0.2%; the risk of hematoma is 1.4%; the risk of infection is so small that the precise number is unknown; and the risk of a loss of superficial sensation is 0.5% (55). After the biopsy,

there is a 50% chance that the subject will experience pain at the biopsy site for 24- 48 hrs. However, over the counter pain medications have been successful in mitigating pain from the biopsy site.

Aim 1: It is important to note the biopsies are in a fasting state (no food since dinner the night before). For the first biopsies in the hospital on the day of surgery, fasting is required per routine care before surgery. For the second biopsies, occurring at one OR two weeks after surgery, fasting may lead to some discomfort. Patients may have to delay taking their pain medication, or risk upset stomach if they take their pain medication without food.

Aim 2: It is important to note the biopsies are in a fasting state (no food since dinner the night before). Fasting may lead to some discomfort. Patients may have to delay taking their pain medication (if taking any), or risk upset stomach if they take their pain medication without food.

Risk from heavy water (Aim #1 only). Brief periods (< 30 minutes) of dizziness have been reported in a small number of people (< 5%) after drinking tracer water. This is due to the tracer water being “heavier” than normal water. “Heavier” water can temporarily disrupt the inner ear’s ability to control balance, producing a sensation of dizziness.

Magnetic stimulation (Aim #1 only). Magnetic stimulation of the peripheral nerve is a safe and non-invasive way of supplying information to the muscle. Because this pulse is magnetic, and not electric, the procedure is painless. No long-term side effects have been reported; however, on rare occasions, individuals find the stimulation uncomfortable.

Magnetic Resonance Imaging (MRI, Aim #1 only). The U.S. Food and Drug Administration (FDA) has set guidelines for magnet strength and exposure to radio waves, and we will carefully observe those guidelines. For the exposure in our ongoing study, no negative effects have been seen. Some people may feel uncomfortable or anxious during the MRI. On rare occasions, some people might feel dizzy, get an upset stomach, have a metallic taste, or feel tingling sensations or muscle twitches. These sensations usually go away quickly. MRI poses some risks for certain people. If an individual has a pacemaker or some metal objects inside the body, the strong magnets in the MR scanner may do harm. Another risk is a metallic object flying through the air toward the magnet and hitting the subject.

Risk from falls. There is a possibility that a participant may fall and hurt yourself during this study. Knee pain may impact a participant’s ability to control muscles. It takes time to heal from this type of surgery and we are asking you to perform physical tasks that may be challenging to you. You will be supervised at all times when completing the tests that help us determine your ability to move and your strength.

Pregnancy risk. The risks of the amino acid supplement to the human embryo or fetus have not been studied. Women who are pregnant are not eligible to participate in this study. Women of potential childbearing age will be asked if they are or could possibly be pregnant. It is possible a hormone pregnancy test will be administered to verify pregnancy status.

Adequacy of Protection Against Risks.

Participant Confidentiality. Described in the Confidentiality section above.

MEND Nutrition, Inc. MEND has the potential as a for-profit supplement company to benefit directly from the outcome of this research. We have purchased the supplement from MEND because MEND's proprietary approach to masking the bittering taste associated with EAAs overcomes a significant barrier to enrollment. MEND is not paying for the study, involved in study design, or execution. MEND has no control over the publication/dissemination of study results. There is no difference between researching EAA supplementation provided by MEND versus another commercial supplement provider such as GNC.

The physicians on this study are not receiving compensation from MEND. Should the nature of this relationship between MEND and any member of the research team (including physicians) change, formal submission per IRB requirements will be executed.

Physical injury. To minimize this risk each subject will be supervised by a member of the research team at all times during testing. All aspects of this proposal are currently used and implemented by the study team.

Blood draws (Aim 1). Each blood tube collected is between 2.7mL and 7.0mL, depending on the blood test requirements. The amount of blood collected at each blood draw is between 28mL and 35mL (high estimate). As reference, when a person donates blood, 500-550mL of blood are donated. Even with seven tubes of blood, the amount collected at each draw is approximately 7% of the amount required at a typical blood donation.

Muscle biopsy. Pain during tissue sampling will be eliminated by anesthesia. Moreover, pain-control measures initiated postoperatively by the research team will be sufficient to control for potential pain at the biopsy sites during inpatient hospitalization (TKA). However, over-the-counter medications such as ibuprofen are sufficient to control such discomfort for all subjects as needed and after the single bilateral biopsies performed at the PI's lab. The risk of bleeding will be reduced with manual direct pressure for 10 minutes or until bleeding has stopped. The risk of infection is minimized by the use of a sterile field. We have performed numerous muscle biopsies in the OR (10, 100) as well as post-operatively at 6 wk post-TKA without incident. Due to the necessity of a fasting state for the one OR two week post-operative biopsies (Aim #1) the study team will accommodate as early as 6:00am for scheduling the biopsies to help minimize any potential discomfort.

Heavy water (Aim #1). Our study coordinators will continually remind subjects via telephone or in person of the potential for balance issues with deuterium oxide (heavy water).

Magnetic stimulation (Aim #1). Participants will be asked to complete a standard Transcranial Magnetic Stimulation Safety Screening Questionnaire. In the event that a subject answers "yes" to one of the questions on the questionnaire, magnetic stimulation will not be used with these participants. If a subject experiences discomfort at any point, this portion of the protocol will be stopped immediately.

There is significant overlap with regards to TMS and MRI safety screening questionnaires (e.g., Do you have a pacemaker?), so, in most cases, people who answer "yes" to a question in the TMS safety screening would be excluded from the study, as they would not qualify for an MRI.

Magnetic Resonance Imaging. All participants will be asked to complete a standard MRI safety screening questionnaire. If it is deemed unsafe for an individual to have an MRI, they will be excluded from the study (see exclusion criteria).

All of the above testing and procedures will be performed either at the hospital where the TKAs are performed (Sacred Heart Medical Center, River Bend), in the PI's lab (which is immediately adjacent to the Sacred Heart Medical Center, University District's Emergency Department), or in the Lewis Center for Neuroimaging (LCNI, location of MRI) (which is 0.5 miles from the Sacred Heart Medical Center, University District's Emergency Department), or Slocum Center for Orthopedics & Sports Medicine located in Eugene.

Risk from falls. Participants will be supervised at all times when completing the tests that help us determine your ability to move and your strength.

Pregnancy risk. Women who are pregnant are not eligible to participate in this study. Women of potential childbearing age will be asked if they are or could possibly be pregnant. It is possible a hormone pregnancy test will be administered to verify pregnancy status.

Data Safety Monitoring Plan

The ultimate responsibility for data and safety monitoring rests with the Principal Investigator. It is equally clear that the institution must promote an environment that facilitates detailed ongoing review and safe conduct of high-priority research studies. Effective data and safety monitoring is not the result of a single committee or individual, but is a shared responsibility within our protocol management scheme. The risk level associated with this study is estimated to be moderate and reasonable.

Plan for Monitoring and Safety Review.

- [name], PT, the Principal Investigator, will be responsible for monitoring the safety environment of the participants during the entire study. The orthopedic surgeon Co-Investigators [name], [name], [name], and [name], will be medically responsible for the subjects' care relative to the surgery and post-operative medical coverage.
- Older subjects will be patients of the Sacred Heart Medical Center, continuously monitored by nursing and hospital staff during inpatient stay after TKA, and followed by the surgeons and research team.
- Thorough monitoring of the recruitment, enrollment, retention, informed consent process, adverse events, study procedures, and evaluation of primary and secondary endpoints will be closely observed by the PI, [name], PT, PhD., and Co-Investigator [name].
- DSMB: We have designed a data and safety monitoring committee and plan. The members of the DSMB will be:

- [name]., PhD
Professor and Director, Graduate Programs in Exercise Science
Department of Health Sciences
- [name]
Associate Professor of Medicine
Co-Director & Senior Statistician, Data Management and Analysis Core of the Pittsburgh
Claude D. Pepper Older Americans Independence Center
- [name]
Professor of Medicine, Cell Biology & Physiology, and Physical Therapy
Assistant Director, Biomedical Mass Spectrometry Research Laboratory

Committee members will participate in the completion of the DSMB Charter, Guidelines, assuring all DSMB items identified by NIH via the DSMB Checklist are satisfied.

Adverse Event Reporting. Adverse Event Grading Scale as defined by the AE reporting form and study stop criterion (See Study Forms, Appendix 2). [name], the Principal Investigator, will be responsible for monitoring and reporting the occurrence of adverse events throughout the study. Subjects will be monitored continuously throughout each testing session, and will be followed by phone or email to verify compliance with study protocol and to monitor for any un-anticipated events.

Anticipated Adverse Events discussed in the Informed Consent Form for this study will include: potential pain, bruising, and/or infection from the blood draws and muscle biopsies and during functional and strength testing. Should an adverse event occur, the Co-Is will be immediately notified and a note will be entered in to the subject's study record using the grading scale listed below.

The research team will follow the IRB Adverse Event Policy on mandatory reporting of Serious Adverse Events (SAEs), and will also report them immediately both orally and in writing to the IRB Program Director or RSA within 24 hours of occurrence or recognition. The PI, [name], PT, PhD, will be responsible for all AE and SAE reporting.

Annual report. [name] will review the protocol on a continuing basis for subject safety and include results of the review in the annual progress reports submitted to the IRB and the appropriate NIH agency as necessary. The annual report will be provided to the Office for the Protection of Human Subjects and will include a list of adverse events.

Content of annual report. The annual report will address: (1) number of adverse events and description of the event; (2) reason for dropouts from the study; (3) number of participants in the study; (4) whether the study should be continued based on the current data collected and the need to achieve the aims stated.

Potential Research Benefits to Participants

The proposed research is based on strong preliminary evidence that EAA reduce post-operative muscle atrophy by 3-fold in the operative and non-operative lower extremities. Further in our pilot studies,

these positive results extended to gains in strength in the non-operative quadriceps—important for long-term ability to normalize function, and to accelerated recovery of functional mobility (stair descent). These data are all derived from older adults. Preserving quadriceps strength is clinically important because poor strength is directly linked to reduced physical function and gait. Quadriceps weakness inhibits balance (84), reduces functional mobility (20, 82), and increases the risk of falls (83) in older adults. Our preliminary data suggest that patients on EAA treatment lost less muscle from their extremities compared to subjects on placebo. An additional potential benefit will be our potential to provide physical therapy to patients without insurance or in instances where the subjects insurance does not pay for the total number of visits we require for this study. These may be considered a potential benefit.

We repeated this study with 39 patients in 2014-2016 and again found the group taking EAA lost less muscle than the placebo group.

Investigator Experience

University of Oregon

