Age-associated muscle dysfunction results from reduced muscle mass, strength, and functional capacity (i.e., sarcopenia) (38). Sarcopenia occurs with normal healthy aging and is associated with an elevated risk for falls, physical disability, and loss of independence (105, 106). Estimated healthcare costs due to sarcopenia in the U.S. in 2000 was \$18.5 billion (60). Reducing the prevalence of sarcopenia by 10% can save \$1.1 billion/year in healthcare costs (60). While sarcopenia progresses at a rate of 1%/year in healthy older males and females, surgeries such as hip and knee replacement, will accelerate sarcopenia (99). The projected increase (nearly 7-fold) in the number of TKA to be performed annually in the U.S. in the coming decades will place a significant burden on our healthcare infrastructure, Medicare and Medicaid. The studies in this research plan are significant because they specifically address a major clinical barrier by mitigating post-operative muscle loss that translates directly into improved strength and functional mobility in older adults. Accelerating functional mobility will help to alleviate a significant economic burden by reducing recovery time, shortening time in clinical care, and halting the acceleration of sarcopenia.

While evidence exists linking EAA to anabolic and catabolic regulation of muscle cell metabolism in healthy subjects (87-89), there is a dearth of experimental data investigating mechanistic adaptations that prevent muscle atrophy and restore function in TKA patients. It is known that EAA stimulates an acute anabolic response in muscle by activating the mTORC1 pathway and increasing fractional rates of protein synthesis (i.e., FSR) (50), and that chronic EAA supplementation elevates fasting rates of muscle protein synthesis in older healthy adults (29). However, studies conducted in healthy populations tell us very little about how muscle cell metabolism is altered following major surgery and if EAA supplementation causes an increase in basal rates of muscle protein synthesis and/or attenuate breakdown. Further, mechanisms linking atrophy prevention with positive functional adaptations in a clinical setting are lacking.

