- **Specific Aim #1 (Biochemistry): Determine if EAA elevates basal rates of muscle protein synthesis by up-regulating anabolic pathways & cyto-protective proteins, and inactivating catabolic pathways in the short-term vs. Placebo.**

Identifying molecular pathways that are up-regulated by EAA are needed in order to uncover potential mechanisms of action. Successful completion of the proposed research will determine the degree to which EAA elevate basal rates of muscle protein synthesis and the extent to which these changes coincide with increases in anabolic (SLC36A2, IGF-I, & VEGF) and cyto-protective (ATF4 & REDD1) pathways. As well, completion of Aim 1 will allow us to determine changes in muscle protein breakdown in parallel with changes in catabolic (FoxO3a) proteins (Fig. 3). We expect these findings will provide mechanistic data on the effects of EAA on muscle cell metabolism and signaling that will help explain how muscle atrophy is prevented and functional mobility accelerated following TKA.

To accomplish Specific Aim #1, subjects will be enrolled pre-operatively and asked to participate in a number of study-related activities designed to isolate the effect of EAA supplementation on muscle protein synthesis. Subjects will consume “heavy water” to aid in quantifying chronic muscle protein synthesis rates while consuming the study EAA supplement. Study specific blood draws, muscle imaging (via MRI) and muscle biopsies will be assessed at regular intervals. Patients will capture accelerometer data and complete three-day food diaries, as well as patient reported outcome measures designed to capture health-related quality of life, knee-specific functioning, pain and the degree to which the patient has an ability engage in total joint pre- and post-operative care. Finally, functional testing will capture patient strength and functional capabilities pre- and post-operatively.

The proposed research design will answer the following questions:

- 1.1 *Does EAA elevate or alter levels of muscle protein synthesis vs. Placebo?*
- 1.2 *Does EAA decrease or alter levels of muscle protein breakdown vs. Placebo?*
- 1.3 *Will EAA inactivate catabolic (FoxO3a) and up-regulate anabolic (SLC36A2, IGF-I, ATF4 and REDD1) pathways vs. Placebo?*
- 1.4 *Does inhibition of angiogenic factors (IFG-1 & VEGF) inhibit a pro-angiogenic response?*
- 1.5 *Does EAA influence markers of inflammation vs. Placebo?*

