Recent results from the Phillips group (128) demonstrated that free-living older males taking 5 grams of Leucine with each meal (3x/day for 3 days), placed on either a low- (RDA; 0.8g protein/kg/day) or high-(1.2g protein/kg/day) protein diet, had elevated basal and post-exercise myofibrillar protein synthesis vs. the same individuals on the same diets (low or high) without supplemental Leucine. Subjects on low-protein and high-protein diets supplemented with 5g of Leucine were not different from one another in this study. The finding has direct implications for our patients who eat less after surgery (37). Data for the Phillips paper were obtained by using D₂O and reflect the rates of myofibrillar synthesis over 3 days in individuals who consumed their normal meals and performed their usual level of activity. This suggests to us that using doses of Leucine closer to 15g/day may have a more profound effect in offsetting muscle autophagy, which can be stimulated by mTORC1, which is activated by Leucine (129).

This will bring us close (13.6g/day) to the 15g/day used by the Phillips group. These more current findings justify modifying our protocol in order to maximize our ability to positively influence patient outcomes.

Participant compliance will be assessed by two primary mechanisms: (1) log-book inspection which the subject will record each supplement ingestion time and (2) empty vial collection. Supplements will be randomly tested for quality control using HPLC to ensure no mixing of samples between groups.

Table 1: Composition of investigational supplement (EAA) and Placebo – Aim 1.

Composition	%	g
Essential Amino Acid		
Histidine	11	2.2
Isoleucine	10	2.0
Leucine	18	3.6
Lysine	16	3.2
Methionine	3	0.6
Phenylalanine	16	3.2
Threonine	14	2.8
Valine	12	2.4
Placebo		
Alanine	100	20

Table 2: Composition of investigational supplement (EAA) and Placebo – Aim 2

Composition	%	g
Essential Amino Acid		
Histidine	5	1.28
Isoleucine	8	1.8
Leucine	32	7.4
Lysine	15	3.6
Methionine	8	1.76
Phenylalanine	13	3.1
Threonine	8	1.9
Valine	9	2.08
Tryptophan	2	0.5
Placebo		
Alanine	100	23.42

Study Aim #1 (Biochemistry).

Aim #1: Determine if EAA elevates basal rates of muscle protein synthesis by up-regulating anabolic pathways & cyto-protective proteins, and inactivating catabolic pathways in the short-term vs. Placebo.

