Randomization Assignments. Aim #1 will consist of 2 groups (N=20/group through protocol completion; EAA vs. Placebo) that are identical in protocol design except for metabolic studies.

Metabolic studies will partition the EAA group into 2 (post-TKA bilateral biopsy at 1 or 2 weeks after

UO IRB Protocol #12272013.024 PeaceHealth Protocol #551187

January 2019

Research
 Compliance Services
 Page | 11
 01/26/2019-11/06/2019

"APPROVED"

surgery) and Placebo group into 2 (post-TKA bilateral biopsy at 1 or 2 weeks after surgery). This will allow us to collapse data by group treatment group; questionnaire, activity, food-log, strength & activation, muscle volume and functional data (this equals N of 20 through protocol completion for EAA and N of 20 for Placebo through protocol completion; 20/group, enough for sex comparison), while enabling us to quantify changes over time in metabolism (D_2O) and at discrete time points after surgery (1 and 2 weeks post) between legs when 80% or more of muscle atrophy is occurring (37).

Primary Biochemical Outcome Measures.

To answer our study questions will be answered using an in vivo experimental design. **The procedure schedule can be referenced in Figure 1 (page 17, following a description of all study-related procedures and measures for Aim #1).**

Deuterium Oxide Ingestion Followed by Muscle Biopsies. Deuterium oxide (D_2O , i.e., heavy water) will be used to quantify chronic (days) muscle protein synthesis rates. D_2O will be ingested (50 ml) three times per day for 7 days leading up to TKA. During TKA surgery, a single biopsy will be obtained in the OR from each leg. Beginning on POD#1 and continuing through week 1 or week 2, subjects will continue ingesting 50 ml of D_2O twice daily. Bilateral biopsies obtained from each leg at 1 *or* 2 weeks post-TKA will be analyzed to determine muscle protein synthesis rates. All subjects will have a total of two biopsies from each leg, in a fasting state. This will allow us to determine the independent effects of supplementation on rates of muscle protein synthesis and breakdown (2H_2O) during the acute and sub-acute period.

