Power analyses. For our power calculations, we have assumed a Type I error rate (α) of $.05$, two-tailed. We based power calculations on effect sizes (d) that we derived from analysis of preliminary data preliminary data and prior studies (10, 30, 32, 33, 36, 41, 51, 113). We calculated d as the standardized mean difference between treatment conditions at follow-up: $d = (x_C - x_T)/S$, where x_C represents the primary outcome mean in the Placebo and EAA conditions and S is the pooled standard deviation, after adjusting x for pretest scores and covariates (sex, tourniquet time, age, body mass index, fat/carbohydrate/protein intake).

We propose to enroll **40 total subjects for Aim 1** who are retained through protocol completion (20/group, EAA and Placebo, randomized to either 1 week or 2 week post-operative biopsies), and **80 total subjects** (40/group, EAA and Placebo) **for Aim 2** who are retained through protocol completion to account for possible attrition and to ensure sufficient power to test the hypotheses that EAA therapy up-regulates basal levels of muscle protein synthesis, and reduces post-operative atrophy bilaterally, preserves quadriceps strength, and improves functional mobility relative to a Placebo condition.

Effect sizes. Effect sizes were as follows: (a) Cell and FSR data: REDD1 $d = 1.24$, SLC36A2 $d = 1.27$, and FSR $d = 1.51$ (FSR calculated from mean change from baseline). The mean effect across outcomes was $d = 1.37$, reflecting large effects. (b) Physiological and functional data (percent change from Baseline to 6 wk): operative quadriceps volume $d = 1.52$, and isometric strength $d = .90$; non-operative quadriceps volume $d = 1.05$, and isometric strength $d = .66$; timed up-and-go test $d = 1.03$, timed stair ascent $d = 1.08$, timed stair descent $d = 1.13$, and six-minute walk test $d = .70$. Mean effect size was $d = 1.01$, reflecting large effects.

Power calculations. Power calculations were based on the sample size and minimally detectable ES (MDES) as follows:

- **Aim #1:** For a sample size of 20 completed subjects/group (10/group for metabolic studies, however, EAA vs. Placebo = 20 total EAA and 20 total Placebo). Aim 1, proposed study can detect

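### Aim 1 claims an effect on basal muscle protein synthesis, but its only synthesis measure integrates days of supplementation and cannot separate basal from post-dose synthesis

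*Combined protocol and SAP*

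**What the plan says.** **The claim.** The Project Summary, the Hypothesis section, and the title and deliverable of Specific Aim #1 all concern basal synthesis. The aim is to "Determine if EAA elevates basal rates of muscle protein synthesis", and the title is repeated at the head of the Study Aim #1 methods. The power section justifies the sample size as sufficient "to test the hypotheses that EAA therapy up-regulates basal levels of muscle protein synthesis".

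**What basal means.** The plan does not define it. Introduction and Background contrasts two things: "It is known that EAA stimulates an acute anabolic response in muscle", and a separate finding that "chronic EAA supplementation elevates fasting rates of muscle protein synthesis in older healthy adults". The preliminary biochemistry section likewise sets the response to a single 20 g dose beside a basal rate in TKA patients of 0.0563 ± 0.008 % per hour.

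**The measure.** Under Primary Biochemical Outcome Measures, heavy water "will be used to quantify chronic (days) muscle protein synthesis rates". The Aim 1 description says that it is taken "to aid in quantifying chronic muscle protein synthesis rates while consuming the study EAA supplement". No other synthesis measure is planned.

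**The question and the analysis.** Question 1.1 and the Aim 1 entry under Data Analysis omit the word basal. They ask about synthesis against Placebo, and about its change from baseline to 1 and 2 weeks after surgery.

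**The concern.** The rate named in the claim is not the rate that is measured. A multi-day labelled rate sums everything synthesised while label is present: fasting hours, meals, the hours after each dose, and recovery from therapy. The plan reads such data this way itself. Of a cited heavy-water study in older men, the Investigational Supplement section says that the data "reflect the rates of myofibrillar synthesis over 3 days in individuals who consumed their normal meals" and kept up their usual activity.

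The plan also says that EAA ingestion acutely stimulates synthesis. A difference between arms in the integrated rate could therefore come from the dose responses alone. The Placebo control does not remove this, because Placebo is alanine and the acute EAA response remains in the between-arm difference.

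At stake is Aim 1's main conclusion. A sustained rise in the basal rate is a different mechanism from a series of short post-dose rises. The Investigational Supplement section also says that Aim 1 results must be reported to the FDA.

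**Working it through.** **Plan's own figure.** The plan gives no figure for the acute response or for the basal share of the integrated rate, so there is nothing to reproduce on this point. The nearest figure is the Aim 1 minimum detectable effect, d > 1.10 at 85% power, two-sided 5%, 20 per group. It does not reproduce: (1.960 + 1.036) × √(2/20) = 0.95. That is a separate matter, and nothing below depends on it.

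**Step 1: is any labelling interval free of supplement?**

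| Window | Heavy water | Supplement |
|---|---|---|
| Before surgery | daily for 7 days | twice daily for the same week |
| After surgery | from day 1 to week 1 or week 2 | from day 1, twice daily, to week 6 |

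(Sources: Investigational Supplement, Primary Biochemical Outcome Measures, Figure 1.) None is. After surgery, doses also follow physical therapy within an hour, and the Physical Therapy section says that this timing is meant to maximise the anabolic effect.

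**Step 2: do the fasted biopsies isolate a basal rate?** No. Fasting fixes the state at sampling. It does not change what was incorporated over the preceding days.

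**Step 3: how much could dose responses add within one window?** Suppose the basal rate is unchanged and each of two daily doses raises synthesis by a fraction r for h hours. The 24-hour rate then rises by

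f = 2 × h × r / 24.

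Both r and h are assumptions; the documents give neither.

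| r | h = 1 | h = 2 | h = 3 |
|---|---|---|---|
| 25% | 2.1% | 4.2% | 6.25% |
| 50% | 4.2% | 8.3% | 12.5% |
| 100% | 8.3% | 16.7% | 25.0% |

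If the ±0.008 is a standard deviation (the text does not say), the standardised difference 0.0563 × f / 0.008 runs from 0.15 to 1.76. This cannot be set directly against the plan's FSR effect of d = 1.51, which comes from change from baseline.

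**Step 4: what survives the planned contrast?** The baseline biopsy is intraoperative, after a week on supplement. Write B for the basal rate, the same in both arms, with f acting in the EAA arm only.

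- *Change score, constant f.* EAA change minus Placebo change = f × (B_post − B_pre). If B does not move between windows, this is zero.
- *Change score, f differing by window.* With B constant, the difference is B × (f_post − f_pre). For example, 6.25% before and 12.5% after leaves 6.25% of B. Therapy-timed dosing occurs only after surgery, so f could differ.
- *ANCOVA with slope β on baseline.* With B constant, the difference is f × B × (1 − β). If β equals the plan's assumed correlations of .50 or .75 (equal variances assumed), the 2.1–25% range shrinks to about 1.0–12.5% or 0.5–6.25%.

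**Step 5: does the baseline separate the two explanations?** No. A true basal rise already present in the pre-operative week enters the same algebra in the place of f and cancels in the same way. The contrast treats both sources alike.

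**The case against.** **The plan discloses what it measures.** The aim text calls the measure chronic and on supplement, and question 1.1 and the analysis text do not say basal. This stands. The mismatch is confined to the summary, hypothesis, aim and power wording.

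**The plan also uses basal for a heavy-water rate.** Of the cited leucine study, it says that participants "had elevated basal and post-exercise myofibrillar protein synthesis". This is the best defence, and it shows that the term is used inconsistently. But there basal is contrasted with post-exercise. Aim 1's post-operative windows include physical therapy with doses timed to it, so they are not basal even in that sense.

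**The acute response may be small here.** A reader might infer that the integrated rate must rise in the EAA arm. The documents do not support that. The background reports a diminished anabolic response in older adults, and says that studies in healthy people reveal little about muscle metabolism after major surgery. The preliminary section says that the effect of TKA under chronic EAA is unknown. The rate can rise; it need not.

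**The planned contrast removes much of a constant rise.** This also stands, as step 4 shows. The 2–25% range describes one labelling window and is not the expected bias in the Aim 1 result.

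**Aim 1 is over.** The Aim #2 recruitment text says that the first part of the study was completed in 2016. Redesign is therefore moot, but interpretation and reporting are not: the January 2019 plan still carries the claim.

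**Conclusion.** The concern holds as a limit on what Aim 1 may conclude. A positive heavy-water result would support an effect of EAA against Placebo on integrated synthesis during supplementation. It could not by itself support raised basal synthesis, because no interval, biopsy or baseline in the design separates basal from post-dose synthesis. This follows from the plan's own text and needs no assumed figure.

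The size is unknown. The 2–25% range rests on assumed responses of 25–100% for 1–3 hours after each of two daily doses. It applies within a labelling window, and a constant rise would largely cancel in the change from baseline.

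Two stronger readings might be inferred and are not supported. One is that EAA has no basal effect; the design leaves that open. The other is that Aim 1 fails to answer its question; question 1.1, as worded, remains answerable. Randomisation, sampling and analysis are untouched.

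**What to change.** In the Project Summary, the Hypothesis, the title and deliverable of Specific Aim #1 (and where the title is repeated in the methods) and the power section, replace basal with *integrated (multi-day) muscle protein synthesis during EAA supplementation*. State there, and in the Aim 1 report, that basal and post-dose contributions are not separated.

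Question 1.1 and the Aim 1 entry under Data Analysis need no correction. Because Aim 1 data collection is complete, disclose the rewording as a post-hoc clarification of interpretation, including in the report to the FDA.

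The cost is a few sentences and a narrower claim.
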